## **Objective:**

To observe the effect of application of topically administered oxygen on risk adjusted

outcomes (healing rates, rate of amputations, post-treatment health complications, cost of care) in 40 diabetic patients with chronic wounds.

This is a pilot study which is intended to collect data to calculate an adequate sample size for a larger registered clinical trial. Eleven subjects were enrolled at The Ohio State University; we intend to enroll 29 more subjects at Indiana University. Due to the small sample size this study will primarily be a feasibility study that will attempt to measure and evaluate differences in the relative theoretical costs of the intervention of topical oxygen therapy on this population and subsequently compare outcomes in areas such as overall health improvements and cost effectiveness.

Primary Outcome: Wound healing rates 16 weeks post treatment as compared to the baseline visit.

Secondary Outcomes: Rate of amputations, post-treatment wound complications such as wound infection, QoL (SF-36), cost of care 16 weeks post treatment as compared to the baseline visit.

For details of outcomes see **STUDY ASSESSMENTS AND PROCEDURES**

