**Table-1: Study Timeline**

Week(s)	0 (Visit 1)	1-3	4 (Visit 2) (+/-2 weeks)	5-7	8 (Visit 3) (+/-2 weeks)	9-11	12 (Visit 4) (+/-2 weeks)	13-15	16 (Visit 5) (+/-2 weeks)
Study Visit	✓		✓		✓		✓		✓
Digital Imaging	✓		✓		✓		✓		✓
Topical oxygen or SoC treatment administered at home	✓	✓	✓	✓	✓	✓	✓	✓	✓

**Study Population:** 40 chronic wound patients with diabetes will be recruited based on study inclusion and exclusion criteria by the research personnel. Patients will be randomized into one of the 2 patient groups: the topical oxygen group and the other half randomized into the comparison group.

A proportionate stratified random permuted block design will be used to generate random assignments to the two groups. The stratification will be based on the proportion of patients expected to be seen at a wound center with Wagner grade 1, 2, or 3. This method will ensure balance across the groups and strata and will also account for the difference in the severity over the course of the study period. The biostatistician at the Center for Outcomes Research in Surgery will prepare the master randomization assignment list. The clinical research coordinator will administer randomization using REDCap.

**Blinding.** This is an open label trial. To reduce bias, the personnel involved in evaluating study outcomes will be blinded to treatment group. The standard of care will be provided by their providers at CWC as part of their routine wound care and will not be blinded to treatment group.

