#### **Inclusion Criteria:**

- 1) Age  $\geq$ 18 years
- 2) Able to give informed consent, willing and able to complete study requirements.
- 3) Diabetic
- 4) Chronic wound **OR** Foot Ulcer:
  - a. Ulcer present by history  $\geq$ 4 weeks at time of enrollment

- b. Compliant with standard wound care regimen
- c. If foot wound, Wagner grade 1 or 2, **–OR–** Wagner grade 3
- d. Ulcer size :  $0.6 \text{ cm}^2$  to  $20 \text{ cm}^2$  and has not decreased in size by more than 30% in previous 2 weeks of the enrollment visit
- 5) Adequate circulatory status, as evidenced by any of the following (for target wound located below the knee):
  - a. Ankle Brachial Index (ABI)  $\geq 0.7$  -  $\leq 1.20$
  - b. If ABI non-compressible (ABI  $> 1.2$ ), then toe brachial Index (TBI)  $> 0.5$
  - c. SPP  $> 30 \text{ mmHg}$
  - d. TcOM  $> 30 \text{ mmHg}$
- 6) At least 4 weeks since revascularization procedure, if one has been performed
- 7) Able to complete Topical Oxygen Therapy 4 days/week for 16 weeks (must be able to remove existing wound dressing and apply TO2 Boot/ treatment, and then re-dress wound)

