##### **a. Initial Visit (Visit 1):**

1. The research staff will screen the patients' medical chart for inclusion and exclusion criteria (current CWC patients only).
2. The informed consent will be presented to the patient.
  - Confirmation of the study eligibility including the inclusion and exclusion criteria will be reviewed with the patient; Subjects who self-refer from outside of the IU system will be asked to sign a release of information form so records can be requested &

reviewed for inclusion/ exclusion criteria.

An ankle brachial index will be completed for subjects with below the knee wounds if not already completed per standard of care since wound onset to confirm study eligibility. Those with an ABI < 0.7 or > 1.2 will be excluded and no further study activities will be completed. These subjects will not be enrolled.

3. Included in this initial (baseline) visit will be:
  - Randomization into one of the 2 study groups per Randomization plan
  - Medical history review
  - Concomitant medication review
  - Wound history review (onset, location, etiology, size, infection status, previous treatments)
  - Digital imaging of ulcer input to Wound Matrix™
    - The digital images will be input into a secure web based wound management program, Wound Matrix™ (Wound Matrix, Inc., Chadds Ford, PA, USA) that will be used for planimetric analysis of wound size.
  - Patient will be asked to complete the quality of life questionnaire (SF-36)
  - Point-of-care testing Hemoglobin A1c will be obtained for all subjects who have not had one completed as SoC within 90 days prior to this visit
4. Patients will also be provided with teaching regarding diabetes, footwear, and wound care.
5. Patients will be given a diary (see example at the end) to log their treatment

**b. 4, 8, 12 Week Visit (+/- 2 weeks):** Subjects will be asked to return to the CWC to complete repeat digital imaging of the ulcer. For those who are receiving wound care at the CWC, as much as possible, study visits will be scheduled in conjunction with regularly scheduled wound care appointments. Additionally, for those randomized to the topical oxygen treatment group, all follow-up visits will be calculated from the first day of topical oxygen therapy. The following will be completed during the study visit:

- Digital imaging of the ulcer to measure the response to therapy
- Any wound or health complications will be noted
- Medication review
- Collection of previous diary

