#### **STUDY ASSESSMENTS AND PROCEDURES**

- a. **Wound Healing rates.** Wound healing rates will be determined from wound area measurement at baseline vs final visit using wound photography and Wound Matrix. Wound Matrix will be used to capture wound image, instantly upload wound images and obtain measurement of wound area data elements at the point of care. Measurement should be performed after debridement if there is one as a part of SoC. Wound matrix is a digital wound measurement

system that utilizes tablet/smartphone camera for taking a digital image of the wound in presence of a standard Ruler for size calibration. The image is automatically tracked and measured. The software tracks the outer perimeters of the wounds using a proprietary algorithm.

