**Statistical Analysis Plan:**

**Sample size.** Although the main objective of this pilot trial is not to detect the significant difference between the two study groups, rather to provide preliminary data for the design of future trial, with sample size of n=40 (n=20 in each arm) could also provide at least 80% power to detect superiority of the TO+SoC treatment success rate (50%) vs. SoC (10%) based on a one-sided Fisher's Exact test at a significance level of 0.05.

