## Statistical analysis.

Univariate analysis will be done using frequencies, mean (SD), median (IQR) to describe the patient cohort. Cumulative incidence of wound healing rates 16 weeks post treatment with 95% confidence interval around the risk estimate will be computed for the two groups (SoC and TO+SoC). Bivariate logistic regression will be used to report the odds of wound healing among those with TO+SoC compared to SoC only. Bivariate analysis to compare secondary outcomes between the groups will be done using Chi-square or Fisher's exact tests for categorical variables and t-tests or Mann-Whitney tests for continuous variables (e.g. QoL ratings from SF-36, costs).

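### The healing comparison is unadjusted, although the objective is risk-adjusted outcomes and baseline wound area, which spans 33-fold at entry, is measured in every patient

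*Combined protocol and SAP*

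**What the plan says.** The Statistical analysis section gives one model for healing: "Bivariate logistic regression will be used to report the odds of wound healing among those with TO+SoC compared to SoC only". It also plans cumulative incidence with 95% confidence intervals per group. No covariate is named there or elsewhere in the plan.

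Five other places bear on this.

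- **Objective.** It begins "To observe the effect of application of topically administered oxygen on risk adjusted" outcomes, with healing rates first in the list. No adjustment variable is named.
- **Inclusion Criteria, item 4d.** Ulcers of 0.6 to 20 cm² are eligible if the ulcer is within that range "and has not decreased in size by more than 30% in previous 2 weeks of the enrollment visit".
- **Study Population (randomisation).** The design is stratified permuted blocks: "The stratification will be based on the proportion of patients expected to be seen at a wound center with Wagner grade 1, 2, or 3". Area is not a factor. Item 4c grades a wound only conditionally ("If foot wound, Wagner grade 1 or 2"), while item 4 also admits other chronic wounds.
- **Initial Visit, item 3.** Images of every patient's ulcer go into a program "that will be used for planimetric analysis of wound size".
- **Study Assessments and Procedures, item a.** "Wound healing rates will be determined from wound area measurement at baseline vs final visit using wound photography and Wound Matrix". The baseline area is therefore part of the outcome measurement itself.

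The Study design section also says that changes in standard care will be considered in the analysis. Those changes happen after baseline and do not concern starting size.

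**The concern.** The comparison is made at a fixed 16 weeks, and wounds enter with very different amounts of tissue to close. For a circular wound, radius = √(area/π), which runs from 0.44 cm at 0.6 cm² to 2.52 cm at 20 cm². That makes area a plausible predictor of healing. The geometry does not prove it.

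If area is prognostic, two things follow. With about 20 patients per arm the groups can differ in starting size by chance, and an unadjusted odds ratio carries that difference. A model that leaves area out also gives up precision that needs no extra data to obtain. Both matter here because the Objective and the Sample size paragraph describe the trial as a source of data for designing a larger one, so the estimate from this single trial is its main product. The stated aim of risk adjustment also has no counterpart in the analysis.

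**Working it through.** **Inputs from the documents.** 20 per arm; success 50% vs 10% (odds ratio 1/(1/9) = 9.0); one-sided Fisher's exact test at 0.05; area 0.6 to 20 cm².

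**Assumed, because the documents are silent.** The spread of ln(area) and the strength of its effect on healing. Both are varied.

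**1. The plan's own figure.** The Sample size paragraph says "with sample size of n=40 (n=20 in each arm) could also provide at least 80% power". Enumerating all 21 × 21 outcomes gives an exact power of 83.7%. The claim is met with no adjustment.

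**2. Chance imbalance in area.** 20/0.6 = 33.3 and ln(33.3) = 3.507. If ln(area) is uniform over the entry range, its SD is 3.507/√12 = 1.01. The SE of the between-arm difference in mean ln(area) is SD × √(2/20), and the 95% limit for the ratio of geometric means is exp(1.96 × SE).

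| SD of ln(area) | SE | 95% limit of ratio | P(ratio ≥ 1.5, either way) |
|---|---|---|---|
| 0.7 | 0.221 | 1.54 | 0.07 |
| 1.01 | 0.320 | 1.87 | 0.21 |
| 1.2 | 0.379 | 2.10 | 0.29 |

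A one-SE imbalance at SD 1.01 is exp(0.320) = 1.38-fold. These figures treat area as unrelated to Wagner grade. Any correlation would let the strata reduce the imbalance somewhat.

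**3. Effect on the unadjusted odds ratio.** Hold the balanced healing rates at 50% and 10%, shift ln(area) by half of ln(1.38) in opposite directions in the two arms (smaller wounds on oxygen), and average the logistic risks over the uniform distribution.

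| Fall in odds per doubling of area | Expected rates | Odds ratio multiplied by |
|---|---|---|
| 1.5-fold | 52.2% vs 9.2% | 1.20 |
| 2-fold | 53.2% vs 8.7% | 1.32 |
| 3-fold | 54.1% vs 8.2% | 1.47 |

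With no area effect the multiplier is 1. An imbalance the other way lowers the odds ratio by roughly the same factor.

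**4. Power with and without log area.** Simulation of 3,000 trials per setting, uniform ln(area), one-sided 0.05 likelihood-ratio tests:

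| Fall in odds per doubling | 50% vs 10% | 35% vs 10% | 60% vs 30% |
|---|---|---|---|
| none | 91.5 → 91.1 | 63.7 → 64.4 | 61.6 → 61.6 |
| 1.5-fold | 91.3 → 92.0 | 62.0 → 64.2 | 61.4 → 64.7 |
| 2-fold | 90.5 → 93.6 | 63.6 → 69.4 | 60.2 → 69.8 |
| 3-fold | 90.5 → 97.0 | 62.3 → 74.3 | 60.0 → 77.7 |

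At the planned effect the gains are 0.7, 3.1 and 6.5 points. A Firth fit with a Wald test (2,000 trials) at the 2-fold setting gave 86.6 → 91.3. At a common 30% healing rate, type I error was about 0.06 with or without adjustment. These figures compare two models with each other and should not be set against the 83.7% for Fisher's test.

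**5. What it could do to the next trial.** Suppose true rates of 35% vs 10%, a 2-fold fall per doubling, and a 1.5-fold imbalance favouring oxygen. Expected rates become 38.9% vs 8.4%. With n per arm = (1.96 + 0.84)² × (p₁q₁ + p₀q₀)/(p₁ − p₀)², for 80% power at two-sided 0.05 (assumed), the true rates need 7.85 × 0.3175/0.0625 ≈ 40. The shifted rates give 7.85 × 0.3146/0.0930 ≈ 27. With 27 per arm and the true rates, 0.25/√(0.3175/27) = 2.31, so power is Φ(2.31 − 1.96) ≈ 64%.

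**The case against.** The strongest reply has four parts.

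**No prognostic evidence.** It is tempting to say that healing is known to depend strongly on starting area. The documents give no such relation, and the slopes above are assumptions. This stands, and it is why the range includes no effect at all.

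**Chance imbalance is ordinary sampling error.** At the planned rates (10/20 vs 2/20) the SE of the log odds ratio is √(1/10 + 1/10 + 1/2 + 1/18) = 0.869, so the 95% interval around 9 is about 1.6 to 49. A factor of 1.2 to 1.5 is modest against that. This stands as to scale. But the imbalance is an observable part of that error, and it can be reduced with data already in hand.

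**It is a pilot.** The plan says that detecting a difference is not its main aim, so a few points of power matter little. This stands for power. It does not dispose of the concern about the estimate, because supplying that estimate is the pilot's purpose.

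**Adjustment changes the estimand.** Even with perfect balance the conditional odds ratio would be 10.3, 13.2 or 21.5 in the three settings, against 9.0 marginally. That shift is at least comparable with the imbalance being corrected, and the next trial's sample size needs marginal proportions. This stands, and the remedy has to deal with it.

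A further limit is that the plan does not define the binary healing event. If it were a relative reduction in area, baseline area would already enter the endpoint and the radius argument would not apply directly. The model would still contain no baseline adjustment.

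**Conclusion.** The point holds as a recommended improvement in precision and in consistency with the plan's own objective. The textual facts are firm: a treatment-only model, a 33-fold entry range, no direct balancing of area, area measured in every patient, and an unmet aim of risk adjustment. The size of the benefit rests on the assumed spread of ln(area) and the assumed area effect. At the planned rates it is about 1 to 6 power points, with larger gains at the smaller effects examined, and essentially nothing if area is not prognostic.

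A reader might infer two stronger things that the documents do not support. One is that the unadjusted comparison is biased or invalid. Randomisation makes it valid on average, and the simulated type I error does not depend on whether area matters. The other is that the trial falls short of its stated power. It does not: any loss is relative to an adjusted analysis. Nor is allocation simple randomisation. It is blocked within Wagner strata, which could balance area indirectly to whatever extent the two are related.

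**What to change.** In the Statistical analysis section:

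- Make the main healing comparison a pre-specified logistic regression on treatment and log baseline area (the Visit 1 Wound Matrix value), fitted by Firth's penalised likelihood. About 20 × 0.50 + 20 × 0.10 = 12 healed wounds are expected, so one covariate is about as much as the data support.
- Report from that model the conditional odds ratio, and also the standardised (marginal) healing risk in each arm and the risk difference with its 95% confidence interval. The standardised figures are the ones to carry into the next trial's sample size.
- Keep the unadjusted comparison as a sensitivity analysis.

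The cost is a few sentences and one degree of freedom, with no new data. The conditional odds ratio will exceed the marginal one when area is prognostic even if the arms are balanced, and the standardised risk difference is there to prevent that from being misread. Naming the covariate now matters because the trial is open label: a covariate chosen after an imbalance has been seen would be data-driven.
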